2. STATISTICAL ASPECTS

2.1. ANALYTICAL STRATEGIES AND STUDY POPULATIONS

Inclusion in the analysis may be discussed for participants who meet, in particular, one of the following conditions:

- Participants who have never received one of the two interventions;
- Participants who withdrew their consent;
- Participants who were wrongly enrolled due to major eligibility criterion(a) not being met

The decision to exclude a participant from the analysis is determined by the Scientific Committee, blinded to intervention group and to participant follow-up after enrolment or randomisation. Research staff analysing the endpoints will remain blinded to allocation to the intervention arm until all analyses are completed.

2.1.1. Primary endpoints

- **Definition**

The primary endpoint is the proportion at risk of HCV infection, as determined by the previously developed and validated HCV-MOSAIC risk score [1], which is compared between the run-in and intervention periods, within each arm.

- **Strategy for the main analysis**

Analyses are performed:

- By intent-to-treat (ITT): including all observations and analysed according to the intervention to which the participants were originally assigned, regardless of which intervention they received. This analysis assumes that any individual who was lost to follow-up did not achieve the primary endpoint (i.e., are at risk of HCV infection). Participants who are mistakenly included due to major eligibility criterion(a) not being met are removed from the analysis.
- By per protocol (PP): including all available observations and analysed according to the intervention to which the participants were originally assigned. This analysis excludes all observations after an individual has been lost to follow-up. Participants who are mistakenly included due to major eligibility criterion(a) not being met are removed from the analysis as well as participants who did not receive the intervention to which they were originally assigned.

- **Sensitivity analysis**

The following sensitivity analyses will be performed;

- Including only MSM who used the assigned intervention(s) (both ITT and PP).
- Including only MSM who were at risk of HCV infection at randomization, as determined by the HCV-MOSAIC score (both ITT and PP).
- Correction for issues in adherence and differential loss to follow-up (only PP): identifying pre-randomisation and post-randomisation covariates that predict adherence to the intervention. Depending on the mechanism of inadequate adherence and loss to follow-up, adjustment for confounding by adherence, g-methods or both will be entertained [2].

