Analyses will be performed by intention to treat (ITT) and per protocol (PP). Both analyses will only include individuals completing the lead-in phase (month-6). ITT analysis is defined by including all observations, while assuming that any individual lost to follow-up did not achieve the primary endpoint. PP analysis is defined by including all available observations, while excluding observations after an individual has been lost to follow-up. Subgroup analysis will also be conducted in order to determine whether individuals with certain characteristics are more likely to have a decrease in HCV-MOSAIC score.

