1.2. TRIAL DESIGN

1.2.1. Study design and methods

This study is an international, multi-centre, phase 2, 3-arm, randomized trial (RT) comparing run-in and intervention periods to evaluate the effect of an online behavioural intervention, a home-based sampling for testing intervention, or both on self-reported behaviours associated with HCV acquisition. The first 6 months of the trial includes follow-up with no intervention (termed the “run-in” period) during which participants receive standard care. At month (M) 6, participants are randomly assigned, with an allocation ratio of 1:1:1, to one of the following three arms: (1) a targeted, online behavioural intervention; (2) a participant-initiated, home-based HCV-RNA self-sampling test service using dried blood spots (DBS); (3) consists of a combination of intervention I and II. Participants continue the intervention for 18 months (termed the “intervention” period) in addition to standard care. During both the run-in and intervention periods, five online questionnaires measuring risk behaviour over the past 6 months are administered (i.e., at M0, M6, M12, M18 and M24 of the study).

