1.4. SAMPLE SIZE

We aim to have a minimum of 78 individuals per arm (total of 234) who complete at least one study questionnaire during the intervention period. Assuming a maximum drop-out rate of 5% during the run-in period, 246 participants in total are needed to be enrolled. We simulated power under varying proportions at risk of HCV infection during the run-in period and absolute risk reduction during the intervention. With a sample size of 78 in each arm, we would have 80% power to demonstrate a statistically significant difference, at a type 1 error of 0.05, of a >22% reduction in the primary endpoint from a 60% proportion at risk of HCV infection during the run-in period.

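### Counting lost men as at risk can act only after M6, so the ITT contrast understates a reduction and can show a false increase; an observed-data ITT run should be reported beside it

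*SAP*

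**What the plan says.** - **Design.** SAP 1.2.1: "At month (M) 6, participants are randomly assigned, with an allocation ratio of 1:1:1, to one of the following three arms". There is no untreated arm. SAP 2.2.2 compares the run-in (M0, M6) with each of M12, M18 and M24 in a random-intercept logistic model, within arm. SAP 3.4.1 compares the two periods and reports odds ratios in both the ITT and PP populations.
- **Who is analysed.** Protocol 9.1: "Both analyses will only include individuals completing the lead-in phase (month-6".
- **ITT rule.** SAP 2.1.1: "This analysis assumes that any individual who was lost to follow-up did not achieve the primary endpoint (i.e., are at risk of HCV infection". Protocol 9.1 has the same rule without the explanatory bracket: "ITT analysis is defined by including all observations, while assuming that any individual lost to follow-up did not achieve the primary endpoint".
- **PP rule.** PP fills nothing in. The SAP version removes wrongly included men "as well as participants who did not receive the intervention to which they were originally assigned".
- **Loss-related sensitivity analysis.** SAP 2.1.1 plans one: "Correction for issues in adherence and differential loss to follow-up (only PP".
- **Case-by-case exclusion.** SAP 2.1: "Inclusion in the analysis may be discussed for participants who meet, in particular, one of the following conditions". Withdrawal of consent is among the conditions listed.
- **Planned loss.** SAP 1.4: "Assuming a maximum drop-out rate of 5% during the run-in period". No rate is given after M6, and neither document defines loss to follow-up.

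**The concern.** In a parallel-group comparison, a missing-equals-failure rule falls on every arm. Here the comparator is the same men's run-in. Nobody in the analysis can be lost before M6, so the rule adds at-risk men to one side of the contrast only. The ITT odds ratio therefore partly measures questionnaire loss, even when loss has nothing to do with risk.

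The stake is not a false claim of benefit. A real reduction may be missed, most easily at M24, and an intervention may appear to have raised risk behaviour.

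The wording adds a smaller problem. The endpoint is being at risk, and *achieving* it means a score of 2.0 or more in Protocol 9.1 and in SAP 2.1.2, 3.4.1 and 3.5.5. Yet the ITT rule says that lost men did not achieve it and means that they are at risk. Nor does either document clearly fix which period is the numerator of the odds ratio.

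**Working it through.** **1. The plan's own figure.** Inputs from SAP 1.4: 78 per arm, 60% at risk in the run-in, an absolute fall of 22 points (to 38%), type 1 error 0.05 (two-sided assumed). For two proportions:

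- pooled SE = √(2 × 0.49 × 0.51 / 78) = 0.0800
- unpooled SE = √((0.60 × 0.40 + 0.38 × 0.62) / 78) = 0.0781
- z = (0.22 − 1.96 × 0.0800) / 0.0781 = 0.81, so power is 79%

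This reproduces the stated 80%. Enrolment of 246 is 234 × 1.05 = 245.7, rounded up.

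**2. Closed form for the fill-in.** Let p be the true intervention-period proportion and d the share filled in. With loss unrelated to risk, the apparent proportion is p + d(1 − p). Odds ratios are intervention over run-in, marginal. The values of d are assumptions.

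| d | No change (p = 0.60) | OR | True fall (p = 0.38) | Apparent fall |
|---|---|---|---|---|
| 5% | 0.60 + 0.05 × 0.40 = 62% | 1.09 | 0.38 + 0.05 × 0.62 = 41.1% | 18.9 points |
| 10% | 64% | (0.64/0.36)/(0.60/0.40) = 1.19 | 44.2% | 15.8 points |
| 20% | 68% | (0.68/0.32)/(0.60/0.40) = 1.42 | 50.4% | 9.6 points |

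Two things would shrink this:

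- If 80% of lost men are truly at risk, the shift is d × 0.20, and the null OR is 1.04 / 1.09 / 1.19 at 5 / 10 / 20% loss.
- If half of the lost men are excluded under SAP 2.1 (assumed), the null proportion is [0.60(1 − d) + d/2]/(1 − d/2) = 61.0 / 62.1 / 64.4%.

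**3. Simulation of the SAP model at M24.** 78 men in one arm; random-intercept SD 1 and 2 (within-person correlation 0.17 and 0.39); M0 and M6 as run-in; loss accumulating to M24 and unrelated to risk; two-sided 5% Wald test; 1000 runs per cell. Each arm is fitted separately, whereas the SAP uses one model with an arm-by-time interaction. Ranges are over the two correlations. Odds ratios are conditional.

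| Loss by M24 | Null: median OR, fill-in | Null: false increase, fill-in | Power for 22-point fall, fill-in | Power, observed data |
|---|---|---|---|---|
| 5% | 1.11–1.15 | 6% | 84–94% | 91–98% |
| 10% | 1.24–1.33 | 9–13% | 71–80% | 91–97% |
| 20% | 1.55–1.77 | 24–31% | 34–41% | 90–95% |

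On observed data the null median OR was 0.99–1.01, with a false increase in 2–4% of runs.

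**4. M12 and pooled contrasts.** These depend on how much loss precedes M12. SAP 1.4 defines the 78 as men with at least one intervention-period questionnaire. If loss is monotone, such men are present at M12. With loss of 0 / 10 / 20% at M12 / M18 / M24, power with fill-in is 95–98% at M12 and 92–97% pooled over M12–M24; M24 is unchanged at 34–42%. With 10 / 15 / 20% instead, the figures are 71–81% at M12 and 76–82% pooled.

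**5. What the planned analyses cover.** For the composite primary endpoint, ITT uses all randomised men but fills in. SAP PP uses observed data but drops men who did not receive their intervention. The sensitivity analyses narrow the sample further or apply to PP only. None of them fits the observed questionnaires of all randomised men.

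**The case against.** - **The rule is a deliberate safeguard.** In an unblinded, self-report, before-after design whose aim is to detect a decrease, treating lost men as failures protects against false benefit. This stands, and it is a reason to keep the run.
- **The alternative can err the riskier way.** This also stands. With no true change and loss concentrated in men currently at risk (80% or all of new losses; 10 / 20% lost by M24), the observed-data model gives a median M24 OR of 0.92–0.96 / 0.83–0.95. False reductions reach 7% at M24 and 9% at M12, against a nominal 2.5%. Under the same loss, fill-in gives 1.13–1.20 / 1.29–1.48. Neither run is unbiased, so the case is for reporting both, not for replacing one.
- **PP is already a check.** Partly true. Protocol 9.1's PP has no exclusion for non-receipt and comes close to the analysis proposed here. The SAP added that exclusion, and the number of men affected is unknown.
- **The correction for loss is limited to PP for good reason.** Fair: once every loss is filled in, nothing is missing in the ITT set.
- **M24 is not the designated primary contrast.** Correct. The M24 figures show where the effect is largest, not the trial's overall power.

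**Conclusion.** The point holds for the within-arm primary contrast. The rule cannot create a false reduction. It shrinks a true one and can produce a false increase, by an amount set by post-M6 loss, which the documents do not give. The sizes rest on assumed 10 / 20% loss by M24, unrelated to risk and all filled in. They are smaller if lost men are mostly at risk or if some are excluded under SAP 2.1.

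Three stronger readings are tempting and not supported:

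- **That the trial loses its planned power overall.** On SAP 1.4's definition of the 78, M12 and pooled power stay above 90% even with 20% loss by M24. Men lost before M12 would come on top of the 78, and Protocol 4.4 lacks this definition, so the matter is open rather than shown.
- **That no planned analysis uses all men's observed data.** This is true only of the composite primary endpoint. SAP 2.2.2 and 3.5.3 plan random-intercept models of the individual score items, which 2.2.2 runs in the overall population with no fill-in rule stated.
- **That lost men will be coded as not at risk.** Protocol 9.1 read literally would do this and turn an unchanged 60% into 54 / 48% at 10 / 20% loss (0.60 × 0.90, 0.60 × 0.80). The SAP bracket rules it out. What remains is a wording conflict to align.

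**What to change.** 1. In SAP 2.1.1, add a co-reported ITT estimate: the planned mixed-effect logistic model on all observed questionnaires of all randomised men, by assigned arm (or multiple imputation from M0, M6 and earlier visits).
2. Present it side by side with the existing run, labelled as a bounding analysis in which lost men count as at risk. Read an apparent increase, or a failure to show a reduction, in light of both.
3. In both documents, replace the phrase about not achieving the endpoint with *counted as HCV-MOSAIC score ≥ 2.0*.
4. Define loss to follow-up, including how a man who misses one questionnaire and returns is handled.
5. State which period is the numerator of the odds ratio.

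The cost is some wording in the SAP and protocol and one extra run of a model already planned; no new data or participants are needed. The downside is that the added run relies on missing at random. With a true 22-point fall, 20% status-linked loss and correlation 0.17, the M24 OR is 0.26–0.29 on observed data and 0.47–0.54 with fill-in, against 0.34 when loss is unrelated to risk. The two runs straddle that value, which is why both must be reported.

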3. STUDY DESIGN

We will perform a multi-center 3-arm randomized trial (RT) evaluating the effect of an online behavioural intervention, a home-based testing intervention, or a combination of both on HCV risk behaviour (**Figure 1**). The trial will start with a 6 month run-in period (standard care). This 6 month run-in period is used to determine at-risk behaviour under no intervention. Including a control comparator arm with no intervention was deemed unappealing to MSM (personal communication, [name], Soa Aids Nederland (NGO)) and could lead to high attrition rates. Hence, we decided that the risk of non-differential loss to follow-up would outweigh any benefit with using a control arm and we opted for a run-in comparison period instead. The intervention period will start at month 6 of the study period. Participants will be randomly assigned to one of the three arms (1:1:1 randomization). During this period, participants will receive standard care plus one or both interventions. Follow-up in the intervention period will end after 18 months. In total, five questionnaire measuring risk behaviour over the past period will be offered online every 6 months in the run-in period and intervention period (i.e., at month 0, 6, 12, 18 and 24 of the study period). This study will be viewed as a pilot approach to evaluate, within each arm, if a significant decrease in at-risk behaviour can be observed during the intervention period.

[figure not shown]

Figure 1: Study design of the ICECREAM study

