2.1.2. Secondary endpoints

- **Definition**

Secondary endpoints are as follows:

- Incidence rate of HCV reinfections during both the run-in (i.e., M0 and M6) and intervention period (i.e., M12, M18, M24), both self-reported and laboratory-confirmed, defined as the number of cases divided by the total person-years of follow-up at risk for reinfection
- Incidence rate of any STI during the run-in and intervention period, both self-reported and laboratory-confirmed, defined as the number of chlamydia, gonorrhoea, genital herpes and/or syphilis infections divided by the total person-years of follow-up
- Other HCV-related risk behaviour during run-in versus intervention period, more specifically:
 - Changes in the mean or median number of sex partners (depending on the distribution of the variable of interest)
 - Changes in the mean or median number of condomless anal sex acts with casual partners (depending on the distribution of the variable of interest)
 - Changes in the proportion of participants reporting any individual behaviours that are included in the HCV-MOSAIC risk score
 - Changes in mean or median sexual wellbeing score (depending on the distribution of the variable of interest)
- The proportion of participants achieving an HCV-MOSAIC risk score ≥ 2.0 at the end of follow-up compared between intervention arms (in both ITT and PP populations)

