2.2.2. Comparative analysis

The primary endpoint is compared between the run-in period (i.e., at M0, M6) and at each time point during the intervention period (i.e., at M12, M18, M24) using a mixed-effect logistic regression model. In this model, each individual serves as their own control and between-individual differences at baseline are accounted for using a random-intercept. Odd ratios (OR) comparing the odds of run-in versus intervention time points, along with their 95% confidence intervals (CI), are estimated and stratified on study arm. These stratified analysis are performed by including an interaction term between arm and study time point (along with their individual covariate) in the model, while study time points are statistically tested within strata of the study arms. Comparisons between run-in and intervention time points are systematically conducted as follows:

- Unadjusted;
- Adjusted on the randomisation strata (country and, if sufficient numbers of individuals in each intervention arm are available, inclusion centre [3]);
- Adjusted on covariates that could potentially affect the evaluation of the primary outcome

Incidence rates of HCV reinfections and STIs are calculated during the run-in and interventions periods, separately. Considering that few HCV reinfections are likely to occur,

we intend to analyse the relative difference in incidence rates between periods using a Bayesian exponential survival regression model with non to weakly informative *a priori* distributions [4, 5]. The relative difference in incidence rates of STIs are compared between periods using a Poisson regression model with ln of person years of observation as an offset. These models are run on both the overall study population and stratified by treatment arm (using the same model configuration of fixed-effect covariates as in the primary endpoint).

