3.5.5. Differences in HCV-MOSAIC risk scores between arms

- **Definition**

The proportion of participants achieving an HCV-MOSAIC risk score ≥ 2.0 at the end of follow-up, compared between intervention arms.

ORs comparing arms and 95%CI are calculated.

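### Restricting the sensitivity analysis to men at risk at M6 selects on a run-in outcome and produces a false within-arm reduction

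*SAP*

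**What the plan says.** SAP 2.1.1 defines the primary endpoint as the proportion with an HCV-MOSAIC score of 2.0 or more, compared between run-in and intervention within each arm. One of its three sensitivity analyses is restricted as follows: "Including only MSM who were at risk of HCV infection at randomization, as determined by the HCV-MOSAIC score (both ITT and PP").

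Three other statements determine what this restriction does:

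- Timing of randomisation (SAP 1.2.1): "At month (M) 6, participants are randomly assigned, with an allocation ratio of 1:1:1".
- Reference period (SAP 2.2.2): "The primary endpoint is compared between the run-in period (i.e., at M0, M6) and at each time point during the intervention period". SAP 3.4.1 uses the same periods.
- Missing follow-up under ITT (SAP 2.1.1): the analysis assumes that "any individual who was lost to follow-up did not achieve the primary endpoint (i.e., are at risk of HCV infection").

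The trial has no untreated arm. Protocol section 3 explains: "Including a control comparator arm with no intervention was deemed unappealing to MSM". The same section gives the aim as "to evaluate, within each arm, if a significant decrease in at-risk behaviour can be observed during the intervention period". Neither document gives the at-risk subset its own reference visit or contrast, so the within-arm model of SAP 2.2.2 applies to it.

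**The concern.** The variable and cut-off that select the men are also the outcome, measured at a visit that belongs to the reference period. Every selected man is at risk at M6 by construction. Some are there because M6 happened to be a high-risk half-year for them, and they would fall back later without any intervention. The random intercept does not repair this, because the model is fitted to a sample already selected on one of its own outcome values.

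A sensitivity analysis should show whether the main result stands under another reasonable choice. This one tends to show a reduction whether or not there is one, so its agreement with the main result would say nothing about robustness. With no untreated arm, nothing within an arm separates the artefact from an effect.

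**Working it through.** **Inputs from the documents.** SAP 1.4 gives 78 men per arm, 60% at risk in run-in, and 80% power at a type 1 error of 0.05 for a reduction of 22%. Read as 60% to 38%, a two-sided comparison of two proportions with 78 per group gives 79.1% power, so the design figure reproduces as an absolute reduction. No figure is stated for the sensitivity analysis. The expected subset is 0.60 × 78 = 46.8, or about 47 men per arm.

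**Assumptions.** There is no intervention effect and no time trend. The within-person correlation ρ between visits six months apart is 0.3, 0.5, 0.7 or 0.8. It is either constant over time or fades as ρ, ρ², ρ³ (first-order Markov).

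**False drop.** With q_k the probability of being at risk k visits from M6, given at risk at M6:

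- constant: q = 0.6 + 0.4ρ
- fading: q_k = 0.6 + 0.4ρ^k
- run-in proportion = (1 + q_1)/2, because M6 is fixed at 1 and M0 has probability q_1
- false drop = (1 + q_1)/2 − q_k

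| | ρ = 0.3 | 0.5 | 0.7 | 0.8 |
|---|---|---|---|---|
| q_1 (M0, M12) | 0.72 | 0.80 | 0.88 | 0.92 |
| Run-in, M0 and M6 | 0.86 | 0.90 | 0.94 | 0.96 |
| Drop, constant (any visit) or fading at M12 | 14 | 10 | 6 | 4 |
| Drop, fading, M18 | 22 | 20 | 14 | 10 |
| Drop, fading, M24 | 25 | 25 | 20 | 16 |

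Drops are in percentage points. Example for ρ = 0.5, fading, at M24: 0.90 − (0.6 + 0.4 × 0.125) = 0.90 − 0.65 = 0.25.

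**Effect of the ITT rule.** With a share L lost, unrelated to risk, and counted as at risk, the later proportion is L + (1 − L)q_k. The drop cancels when L = [(1 + q_1)/2 − q_k]/(1 − q_k). That is 50% under constant correlation, and 64 / 71 / 77 / 80% at M24 under fading. With an assumed 10% loss and constant correlation the drop is still 11 / 8 / 5 / 3 points.

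**False significance.** Null arms of 78 men were simulated (800 per value) and restricted to those at risk at M6. A random-intercept logistic model was fitted, and a reduction counted when Wald z < −1.96 (nominal 2.5%). Simulation error is up to 1.8 points. Ranges under constant correlation reflect two ways of generating the data.

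| Falsely significant reductions (%) | ρ = 0.3 | 0.5 | 0.7 | 0.8 |
|---|---|---|---|---|
| Constant, per time point (SAP model) | 54-62 | 43-49 | 27-29 | 16-18 |
| Constant, later visits pooled | 79-82 | 64-69 | 40-41 | 23 |
| Constant, ITT with 10% loss, per time point | 40-43 | 31-33 | 17-19 | 10-12 |
| Fading, M24 | 91 | 95 | 92 | about 80-85 |

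The null OR is about 0.30-0.36 under constant correlation, and 0.22 / 0.14 / 0.09 / 0.07 at M24 under fading. A separate simulation with normal random intercepts (correlation 0.17 / 0.39 / 0.54), pooled later visits and a two-sided likelihood-ratio test gave median OR 0.36 / 0.35 / 0.33. It rejected in 89 / 74 / 67% of arms, always as a reduction.

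**Unselected comparison.** Under the same nulls the main analysis gives OR 0.95-1.04. False reductions are 1-4% (constant) and 1-8% (fading, where the OR stays near 1).

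**The case against.** The mechanism is hard to dispute. The case on the other side concerns weight and remedy.

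- *It is one supporting analysis in a trial the protocol calls a pilot.* This stands: no primary conclusion rests on it alone, and at a constant correlation of 0.8 the drop is only 4 points.
- *The largest figures rest on an assumed Markov decay.* This also stands. At ρ = 0.3 that model implies a correlation of 0.027 after 18 months, which is extreme for habitual behaviour. The random-intercept model of SAP 2.2.2 corresponds to the constant case, so those figures should lead. They already show the fault.
- *The ITT rule works against the bias.* It does, but cancelling it takes 50% loss or more, and the PP version has no such offset.
- *An M0-only reference would keep the within-arm objective.* Under constant correlation it is unbiased (OR 1.00, 0.5-2.5% false reductions per time point). Under fading it leaves q_1 − q_3 = 11 / 15 / 14 / 12 points at M24, with 22 / 47 / 53 / 48% false reductions. It is defensible only as a labelled supplement.
- *A between-arm contrast answers a different question, with little power.* This is a real cost: two equally effective arms would show no difference. It is still the contrast in this subset that randomisation protects.

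**Conclusion.** The concern holds. As written, the at-risk-at-M6 analysis is biased towards a reduction in every arm unless behaviour never changes between visits or loss is large enough for the ITT rule to cancel the drop. With 60% at risk and constant correlation of 0.3 to 0.8, the false drop is 14 to 4 points. The false-positive rate per time point is about 54-62% down to 16-18%, against 2.5%. With fading correlation the drop at M24 is 25 to 16 points. The correlations are assumptions, and so is loss unrelated to risk in the ITT figures.

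The fault is confined to this sensitivity analysis and should be fixed before its result is interpreted. The M6-only reference in Protocol 9.1 is not applied to this subset by either document, so no figure is given for that combination.

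**What to change.** In SAP 2.1.1, for this subset only:

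1. Replace the within-arm test with the comparison of at-risk status "at the end of follow-up compared between intervention arms", which SAP 2.1.2 and 3.5.5 already plan for the whole population. M12 and M18 can be added. In 20,000 null trials per correlation value, the two-sided type I error of this test at M24 in the subset was 4.4-6.3%.
2. Show run-in and intervention proportions descriptively only, labelled as subject to regression to the mean. An M0-only within-arm contrast may be added as a labelled supplement.
3. Define M6 status from a questionnaire completed before allocation is shown, and report how many were completed afterwards. Protocol 7.2 reveals allocation at once, and Protocol 7.3 allows questionnaire reminders up to three weeks. Table 1 lists the questionnaire above randomisation, and Protocol 9.1 requires completion of the month-6 lead-in, but neither states the order. This is a safeguard for the between-arm contrast and not part of the bias above.

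The cost is two or three sentences and a check of time stamps, with the same data and software. The within-arm test in this subset is given up, and the subset then informs only relative effects. With 47 men per arm, 80% power at one visit needs a difference of about 22-28 points. With an assumed 10% loss it needs about 24-30 points if the lost are excluded (42 per arm), or about 25-31 if they are counted as at risk. These ranges are for constant correlation.
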